		13.2.1 Documentation	
	12.2	13.2.2 Case Report Form Procedures	
	13.3	MODIFICATION OF PROTOCOL	
14		ERENCES	
APP	ENDIX		
		VERSION 4.0	
	ENDIX		
	ENDIX		
	ENDIX		
APP	ENDIX		
		FFFCTS	50

In-Text Tables

Table 1.	Treatment schema	27
Table 2.	LY3023414 Dose Reduction Levels	29
Table 3.	Prexasertib Dose Modification Levels	30
Table 4.	Additional dose adjustment guidance for prexasertib	30

SYNOPSIS

Summary:

Seventy to 80% of breast cancers have a basal gene expression profile which is characterized by homologous recombination deficiency (HRD) and high proliferation. HRD leads to upregulation of the activity of the non-homologous end joining (NHEJ) error-prone pathway that repairs DNA double strand breaks, a process required for TNBC survival. The hypothesis of this pilot trial is that administration of LY3023414 and prexasertib will inhibit NHEJ in metastatic TNBC. A patient with an exceptional complete and durable response of her primary-refractory metastatic TNBC with PI3K pathway inhibition followed at disease progression by nab paclitaxel/cisplatin provides the clinical rationale for the present trial which will utilize LY3023414 and prexasertib to inhibit HR proficiency in pretreated metastatic TNBC patients.

Patients will be treated with 150 mg LY3023414 PO BID and prexasertib 80 mg/m² IV administered every 2 weeks until disease progression or unacceptable toxicity. Metastatic TNBC patients will undergo core needle biopsies of a metastatic lesion at study entry, and any time after the completion of Cycle 2 of the treatment combination, or at the physician's discretion. If a research biopsy from a patient's metastatic disease cannot be safely obtained, a skin biopsy is permitted. Treatment will be discontinued in patients who achieve a confirmed clinical complete response, and these patients will be followed to document the durability of the complete responses.

Patients whose disease does not respond to prexasertib may be treated with standard of care breast cancer therapies **off study**, at the recommendation of the treating physician.

Objectives:

The primary objective of this study is to assess the objective response rate (CR+PR) associated with LY3023414 and prexasertib in metastatic TNBC patients.

The secondary objectives of this protocol are:

- 1. To assess the duration of response to combination treatment with LY3023414 and prexasertib in metTNBC pts.
- 2. To assess the serial metastatic TNBC biopsy for homologous recombination deficiency (HRD) by evaluating inactivating mutations in HR genes on Next Generation Sequencing (NGS), by evaluating the overall and pattern-specific mutational load in the cancers on NGS, and by assessing H2AX expression by RPPA.
- To assess expression of phosphorylated nuclear EGFR, AKT, DNA-PK and other proteins involved in HR as well as activation of the PI3K, MAPK and JAK/STAT pathways in baseline metTNBC tissues on reverse phase protein arrays (RPPA) as possible predictors of clinical antitumor response to LY3023414 and prexasertib.

Number of patients: 10

Inclusion Criteria:

A patient will be considered for enrollment in this study if all the following criteria are met:

- 1. Patients ≥18 years of age. Patients must agree to use one highly effective (less than 1% failure rate) method of contraception or use a combination of two effective methods of contraception during treatment with study drug and for at least 12 weeks following the last dose of study drug.
- 2. Have a diagnosis of metastatic TNBC previously treated with standard anthracycline, cyclophosphamide, and taxane chemotherapy, unless there was a contraindication to doxorubicin, in which case prior treatment with this agent is not required. **NOTE:** TNBC defined as ER-negative tumors with ≤10% tumor nuclei immunoreactivity, or "ER Low Positive" as defined by the updated ASCO/CAP guidelines 2020.
- 3. Have not received more than 3 prior chemotherapy regimens for metastatic disease. Prior platinum and/or taxane therapy in the adjuvant or metastatic setting is permitted.
- 4. Have locoregional (eg, breast, chest wall, regional lymphatic) or pulmonary or hepatic metastatic disease that is amenable to core needle biopsy. If a research biopsy from a patient's metastatic disease cannot be safely obtained, a skin biopsy is permitted. If a skin biopsy cannot be safely obtained, patients may still be eligible, per physician discretion.
- 5. Have an Eastern Cooperative Oncology Group (ECOG) performance status of 0-2 (See Appendix I)
- 6. Have adequate hematologic function, defined by:
 - a. Absolute neutrophil count (ANC) >1500/mm³
 - b. Platelet count ≥100,000/mm³
 - c. Hemoglobin ≥9 g/dL
- 7. Have adequate liver function, defined by:
 - a. AST and ALT \leq 2.5 x the upper limit of normal (ULN) or \leq 5 x ULN in presence of liver metastases
 - b. Total bilirubin <1.5 x ULN
- 8. Have adequate renal function, defined by:
 - a. Serum creatinine ≤1.5 x ULN or calculated creatinine clearance of ≥60 ml/min
- 9. Have the ability to swallow oral medications
- 10. Patients who have a history of brain metastasis are eligible for the study provided that all the following criteria are met:
 - a. Brain metastases which have been treated
 - b. Off-treatment with steroids for 2 weeks before administration of the first doses of LY3023414 and prexasertib
 - c. No ongoing requirement for dexamethasone or anti-epileptic drugs
 - d. No clinical or radiological evidence of progression of brain metastases
- 11. Patient must be accessible for treatment and follow-up.
- 12. All patients must be able to understand the investigational nature of the study and give written informed consent prior to study entry.

Exclusion Criteria:

A patient will be ineligible for inclusion in this study any of the following criteria are met:

- 1. Have a family history of long QT Syndrome and serious cardiac conditions.
- 2. Have QTcF interval of >470 msec on screening electrocardiogram (ECG) as well as on predose Cycle 1 Day 1 ECG
- 3. Have insulin-dependent diabetes mellitus. Patients with a type 2 diabetes mellitus are eligible if adequate control of blood glucose level is obtained by oral anti-diabetics as documented by HbA1c <8%. Patients with type 1 diabetes mellitus are not eligible.
- 4. Previous radiotherapy for metastatic disease completed <2 weeks prior to study treatment initiation.
- 5. Women who are pregnant or lactating.
- 6. Patients who have any severe and/or uncontrolled medical conditions or other conditions that could affect their participation such as:
 - a. severe impaired lung functions as defined as spirometry and DLCO that is 50% of the normal predicted value and/or O₂ saturation that is 88% or less at rest on room air
 - b. liver disease such as cirrhosis or severe hepatic impairment (Child-Pugh class C).
 - c. viral hepatitis or HIV.
- 7. Concurrent use of CYP3A4 inhibitors and inducers from 72 hours prior to initiation of study treatment until the end of treatment.
- 8. History of any other disease, physical examination finding, or clinical laboratory finding giving reasonable suspicion of a disease or condition that contraindicates use of an investigational drug, or that might affect interpretation of the results of this study, or render the patient at high risk for treatment complications.
- 9. Patients who have received prior PI3K or CHK therapy.
- 10. Any other investigational or anti-cancer treatments while participating in this study
- 11. Any other active malignancy.

Medication and Doses:

This exploratory open label pilot trial will evaluate the administration of LY3023414 and prexasertib in patients with metastatic TNBC.

Metastatic TNBC patients will consent to and undergo core needle biopsies of a metastatic lesion for NGS, RPPA and other molecular analyses at study entry.

Patients will then be treated with 150 mg LY3023414 PO BID and prexasertib 80 mg/m² IV administered every 2 weeks until disease progression or unacceptable toxicity. Any time after the completion of Cycle 2 of the treatment combination, or at the physician's discretion, a second core needle biopsy of the same metastatic lesion (or different metastases if the initial metastasis has regressed) will be performed for RPPA and other molecular analyses. If a research biopsy from a patient's metastatic disease cannot be safely obtained, a skin biopsy is permitted.

Treatment will be discontinued in patients who achieve a confirmed clinical complete response, and these patients will be followed to document the durability of the complete responses.

	Patients whose disease does not respond to the combination of LY3023414 and prexasertib may be treated with standard of care breast cancer therapies off study , at the recommendation of the treating physician.		
Duration of Study:	The duration of patient participation in the study will be a maximum of 18 months.		
Efficacy Assessments: CR, PR, SD, PD		Safety Assessments: Toxicity	

PART I – CLINICAL TRIAL PROTOCOL

1 INTRODUCTION

1.1 BACKGROUND ON TRIPLE NEGATIVE BREAST CANCER

Breast cancer is the most common malignancy in women worldwide, with incidence rates as high as 89.7 per 100,000 women. Although there have been a number of important treatment advances in recent years, and overall mortality is declining due to earlier detection and more effective treatment of early stage disease, metastatic breast cancer (MBC) remains incurable and is the second leading cause of cancer deaths among women.²

Triple-negative breast cancer (TNBC) is defined by the absence of ER, PgR, and HER2 receptor expression. By hierarchical clustering of gene expression patterns, these cancers most often segregate with the "basal-like" intrinsic subtype.³ Compared with other breast cancer subtypes, TNBC is associated with a worse prognosis, including a shorter time to recurrence in early-stage disease, and a shorter time between recurrence and death in the metastatic setting.⁴ Because currently available targeted therapies such as endocrine or HER2-targeted agents are ineffective against this breast cancer subtype, treatment options for TNBC are limited to chemotherapy at this time. To date, no clear molecular target has been identified and proven to have therapeutic value.

1.2 HOMOLOGOUS RECOMBINATION DEFICIENCY IN BREAST CANCER

Seventy to 80% of breast cancers have a basal gene expression profile which is characterized by homologous recombination deficiency (HRD) and high proliferation. HRD leads to upregulation of the activity of the non-homologous end joining (NHEJ) error-prone pathway that repairs DNA double strand breaks, a process required for TNBC survival. A key nuclear enzyme that orchestrates NHEJ is DNA-Dependent Protein Kinase catalytic subunit (DNA-PKcs), a member of the PI3K super-family.

Nuclear Epidermal Growth Factor Receptor (EGFR) is activated by phospho-AKT and both nuclear EGFR and nuclear AKT phosphorylate and activate DNA-PK to promote NHEJ-mediated repair of DNA double-strand breaks. Loss of HR proficiency, which occurs in most TNBCs (the basal-like TNBCs), leads to increased EGFR expression in mammary epithelial cells. However, it is not known whether activated, nuclear EGFR T564 and nuclear AKT that phosphorylate DNA-PK are increased in the setting of HRD in chemotherapy-resistant TNBC.

BEZ-235 is a potent inhibitor of DNA-PKcs, as well as PI3K and TORC1/2, which inhibits NHEJ-mediated DNA double strand break repair, sensitizing cancers to DNA damaging agents. A phase I trials of the sachet formulation of BEZ-235 demonstrated that BEZ-235 was safe with manageable toxicities (including mild to moderate fatigue, nausea, diarrhea, hyperglycemia, stomatitis and anemia) and had demonstrated antitumor activity against breast cancer. However, although the mechanisms behind its activity were compelling, clinical development of this agent was stopped because of highly unpredictable intrapatient bioavailability that could not be overcome with various formulations (Novartis Oncology, personal communication, October, 2015).

Another mechanism which inhibits DNA repair response is the dual inhibition of mTORC1/2. In preclinical studies, the dual inhibition of mTORC1 and mTORC2 decreased DNA repair response as well as decreased the activity of AKT. This dual inhibition allowed for the partial resensitization of platinum-resistant ovarian cancer cells both in vitro and in vivo to platinum chemotherapy, as compared to single inhibition of mTORC1. Blockade of the mTOR complexes may be a novel strategy to sensitize cancers to DNA damaging agents.

1.3 LY3023414

The phosphatidylinositol 3-kinase/mammalian target of rapamycin (PI3K/mTOR) pathway has been reported as activated in >70% of human cancers and has emerged as a promising target for anticancer therapies. PI3K/mTOR signaling plays a central role in regulating physiological processes such as growth, survival, proliferation, and metabolism as well as in the development of malignant disease. Aberrations in PI3K/mTOR signaling by various mechanisms have been described, which lead to increased tumor proliferation, inhibition of apoptosis, and angiogenesis in preclinical models. In cancer patients, genes involved in signal transduction through the PI3K/mTOR pathway may harbor mutations more commonly than any other pathway regulating cell growth and survival. Such mutations are reported to occur in breast, colon, ovarian, gastric, prostate, mesothelioma, endometrial, brain, and lung cancers. Such as a promising target for anticancer through the processes are provided in signal transduction through the processes are provided in signal transduction through the processes.

LY3023414 is an oral PI3K/mTOR inhibitor which selectively inhibits class I PI3K isoforms, mTOR, and DNA-PK via an ATP-competitive mechanism of action. ¹⁴ In vitro, LY3023414 demonstrated a cytostatic antiprofilerative effect, with cells accumulating in G1; no induction of apoptosis was observed. Strong pathway inhibition (ie, dephosphorylation of PI3K/AKT/mTOR pathway downstream substrates [AKT, S6K, S6RP, and 4EBP1]) was observed. Dose-responsive inhibition of tumor growth was observed in preclinical xenograft models when LY3023414 was administered as a single agent, in addition to synergistic antiproliferative effects when LY3023414 was combined with standard of care agents. ¹⁴

The first-in-human study of LY3023414 is a phase 1 trial that was conducted in adult patients with advanced solid tumors refractory to standard therapies. As of September 2014 (reported at ASCO 2015), a total of 47 patients had received LY3023414 either QD or BID. Common treatment-related adverse events (all grades) included nausea (38%), fatigue (31%), vomiting (27%), and diarrhea (17%). A durable partial response was observed in one patient with endometrial cancer which harbored both PIK3R1 and PTEN mutations, and 22 additional patients (47%) had stable disease as their best response. LY3023414 is currently being studied in tumor-specific expansion cohorts for mesothelioma, breast cancer, indolent Non-Hodgkin Lymphoma and squamous NSCLC. LY3023414 appears to be safe when administered as single agent up to 325 mg QD or 200 mg BID. The recommended phase 2 dose for single-agent LY3023414 is 200 mg PO BID, based on safety, tolerability, PK/PD, and preliminary antitumor activity. 15

1.4 PREXASERTIB (FORMERLY LY2606368)

CHK1 is a serine threonine protein kinase that is required for checkpoint-mediated cell cycle arrest to allow for the activation of DNA repair, once DNA damage has been detected. ^{16,17} Preclinical studies in triple negative breast cancer ¹⁷ and head and neck cancer ¹⁸ have demonstrated that CHK1 inhibitors can augment the cytotoxic effects of DNA-damaging

treatments. The loss of CHK1 leads to HRD and therefore to a strong dependence on NHEJ, and the dual inhibition of CHK1 and NHEJ would create a synthetically lethal event. ¹⁹ In addition, cell lines deficient in the Fanconi anemia DNA repair pathway (homologous recombination) have been shown to be hypersensitive to CHK1 inhibition, such that inhibiting CHK1 is synthetically lethal to these cells. ²⁰

Prexasertib (previously LY2606368) is an ATP-competitive protein kinase inhibitor that showed selectivity to CHK1. Preclinical studies in SCLC¹⁶ demonstrated that prexasertib had notable single-agent activity, enhanced cisplatin cytotoxicity in platinum-resistant models, and when combined with the PARP inhibitor olaparib, caused tumor regression and increased survival. Prexasertib recently completed phase I testing, which demonstrated tolerability as well as single-agent clinical activity in a subset of solid tumors.¹⁶ In a single arm, phase II pilot trial in BRCA wild type triple negative breast cancer patients, prexasertib exhibited modest single agent activity, warranting further evaluation as part of combination therapy.²¹

A recent study of single-agent prexasertib in recurrent high-grade serous or high-grade endometrioid ovarian carcinoma demonstrated tolerability and clinical activity.²² Twenty-eight women were enrolled in the study and received at least 1 dose of prexasertib; 79% of patients had disease that was platinum-resistant or platinum-refractory. Of the 28 patients, 24 were assessable per protocol and RECIST response. Eight (33%) of 24 patients had partial responses, which were identified during the first tumor reassessment (in the intent-to-treat population, 8 [29%] patients of 28 had partial response). Median progression-free survival was 7.4 months in the 24 assessable patients, and the most commonly reported adverse event was neutropenia in 26 (93%) of 28 patients. This proof-of-concept, phase 2 prexasertib study in ovarian cancer with encouraging findings warrants further development and validation.²²

1.5 LY3023414 AND PREXASERTIB IN COMBINATION

Dual inhibition of the CHK1 and PI3K/mTOR signaling pathways may disrupt homologous recombination repair. In prexasertib-resistant TNBC PDX models, the PI3K/AKT signaling pathway is transcriptionally elevated. In a nonclinical model, synergistic antitumor activity was observed when prexasertib was combined with a PIK3K/mTOR inhibitor.²³

In a Phase 1b dose-escalation study, LY3023414 and prexasertib were given simultaneously in patients with advanced and/or metastatic cancer. Pharmacokinetic properties for each coadministered agent were consistent with monotherapy PK profiles. Doses recommended for LY3023414 is 150 mg BID, while prexasertib recommended dose is 105 mg/m². The most common adverse events were neutropenia, thrombocytopenia, anemia, nausea, and fatigue. These toxicities were consistent with the respective monotherapy profiles, although the incidence was higher. Supportive care may be required. The combination showed preliminary efficacy in solid tumors; in TNBC, 25% of patients had a partial response, and 37.5% had stable disease.²³

1.7 RATIONALE

The hypothesis of this pilot trial is that administration of LY3023414 and prexasertib will inhibit NHEJ in metastatic TNBC. The exceptional responder patient's treatment history described in the Introduction provides the clinical rationale for the present trial which will utilize LY3023414 and prexasertib to inhibit HR proficiency. The trial will include in depth analysis of the patients' TNBC genome and phosphoproteome to evaluate HR-proficiency and deficiency, and nuclear proteins that drive NHEJ: at baseline and any time after completion of Cycle 2 of the treatment combination, or at the physician's discretion.

2 TRIAL OBJECTIVES

2.1 PRIMARY OBJECTIVES

The primary objective of this study is to assess the objective response rate (CR+PR) associated with LY3023414 and prexasertib in metastatic TNBC patients.

2.2 SECONDARY OBJECTIVES

The secondary objectives of this protocol are:

- 1. To assess the duration of response to combination treatment with LY3023414 and prexasertib in metTNBC pts.
- 2. To assess the serial metastatic TNBC biopsy for homologous recombination deficiency (HRD) by evaluating inactivating mutations in HR genes on Next Generation Sequencing (NGS), by evaluating the overall and pattern-specific mutational load in the cancers on NGS, and by assessing H2AX expression by RPPA.
- 3. To assess expression of phosphorylated nuclear EGFR, AKT, DNA-PK and other proteins involved in HR as well as activation of the PI3K, MAPK and JAK/STAT pathways in baseline metTNBC tissues on reverse phase protein arrays (RPPA) as possible predictors of clinical antitumor response to LY3023414 and prexasertib.

3 STUDY DESIGN

This exploratory open label pilot trial will evaluate the administration of LY3023414 and prexasertib in patients with metastatic TNBC.

Metastatic TNBC patients will consent to and undergo core needle biopsies of a metastatic lesion for NGS, RPPA, and other molecular analyses at study entry.

Patients will then be treated with 150 mg LY3023414 PO BID and prexasertib 80 mg/m² IV administered every 2 weeks until disease progression or unacceptable toxicity. Any time after the

completion of Cycle 2 of the treatment combination, or at the physician's discretion, a second core needle biopsy of the same metastatic lesion (or different metastases if the initial metastasis has regressed) will be performed for RPPA and other molecular analyses. If a research biopsy from a patient's metastatic disease cannot be safely obtained, a skin biopsy is permitted.

Treatment will be discontinued in patients who achieve a confirmed clinical complete response, and these patients will be followed to document the durability of the complete responses.

Patients whose disease does not respond to the combination of LY302314 and prexasertib may be treated with standard of care breast cancer therapies **off study**, at the recommendation of the treating physician.

4 SELECTION OF PATIENTS

4.1 SAMPLE SIZE

Ten patients with metastatic TNBC will be enrolled over 12-18 months.

4.2 INCLUSION CRITERIA

A patient will be eligible for inclusion in this study if **he or she** meets **all** of the following criteria:

- 1. Patients ≥18 years of age. Patients must agree to use one highly effective (less than 1% failure rate) method of contraception or use a combination of two effective methods of contraception during treatment with study drug and for at least 12 weeks following the last dose of study drug.
- 2. Have a diagnosis of metastatic TNBC previously treated with standard anthracycline, cyclophosphamide, and taxane chemotherapy, unless there was a contraindication to doxorubicin, in which case prior treatment with this agent is not required. **NOTE:** TNBC defined as ER-negative tumors with ≤10% tumor nuclei immunoreactivity, or "ER Low Positive" as defined by the updated ASCO/CAP guidelines 2020.²⁵
- 3. Have not received more than 3 prior chemotherapy regimens for metastatic disease. Prior platinum and/or taxane therapy in the adjuvant or metastatic setting is permitted.
- 4. Have locoregional (eg, breast, chest wall, regional lymphatic) or pulmonary or hepatic metastatic disease that is amenable to core needle biopsy. If a research biopsy from a patient's metastatic disease cannot be safely obtained, a skin biopsy is permitted. If a skin biopsy cannot be safely obtained, patients may still be eligible, per physician discretion.
- 5. Have an Eastern Cooperative Oncology Group (ECOG) performance status of 0-2 (See Appendix I)
- 6. Have adequate hematologic function, defined by:
 - a. Absolute neutrophil count (ANC) >1500/mm³
 - b. Platelet count $\geq 100,000/\text{mm}^3$
 - c. Hemoglobin ≥9 g/dL
- 7. Have adequate liver function, defined by:
 - a. AST and ALT \leq 2.5 x the upper limit of normal (ULN) or \leq 5 x ULN in presence of liver metastases

- b. Total bilirubin ≤1.5 x ULN
- 8. Have adequate renal function, defined by:
 - a. Serum creatinine ≤ 1.5 x ULN or calculated creatinine clearance of ≥ 60 ml/min
- 9. Have the ability to swallow oral medications
- 10. Patients who have a history of brain metastasis are eligible for the study provided that all the following criteria are met:
 - a. Brain metastases which have been treated
 - b. Off-treatment with steroids for 2 weeks before administration of the first doses of LY3023414 and prexasertib
 - c. No ongoing requirement for dexamethasone or anti-epileptic drugs
 - d. No clinical or radiological evidence of progression of brain metastases
- 11. Patient must be accessible for treatment and follow-up.
- 12. All patients must be able to understand the investigational nature of the study and give written informed consent prior to study entry.

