8.2 ASSESSMENTS DURING TREATMENT

The following assessments will be performed during therapy on Day 1 prior to the start of each cycle, unless otherwise specified. A Cycle is defined as 28 days (prexasertib dosing on Day 1 and 15).

There is a window (**up to 4 calendar days prior to the scheduled time point**) for assessments during the study. Any delay within this window is NOT a deviation. Assessments that are to be done on days when study drug is administered must be done **prior to dosing** as these assessments (CBC, CMP, assessment of response, etc) may determine whether or not drug is administered, or if a dose reduction is necessary, unless otherwise noted.

Note for Cycle 1 only: the prestudy assessments that correspond to assessments below may be used as Cycle 1 assessments as long as they are completed within the 72 hours prior to the patient receiving their first dose of study drug. If more than 72 hours have elapsed since the prestudy assessment, the assessment must be repeated for Cycle 1.

- 1. A brief medical history, to capture events that have occurred since the last cycle. Events that were not captured in the baseline complete medical history should be recorded on the AE page of the CRF.
- 2. A brief physical examination, including vital signs and body weight
- 3. ECOG PS (Appendix III)
- 4. Assessment of concomitant medications
- 5. A CBC with differential and platelet count on Day 1 and Day 15 of every cycle
- 6. A CMP Day 1 and Day 15 of each cycle
- 7. Assessment of magnesium (Mg) and phosphorus (P) Day 1 and Day 15 of each cycle
- 8. HbA1c must be obtained Day 1 and Day 15 of each cycle
- 9. Fasting serum glucose must be obtained Day 1 and Day 15 of each cycle
- 10. A pre-dose ECG (within 10 minutes of beginning prexasertib infusion) must be obtained on Cycle 1 and Cycle 2. Additional ECG may be obtained if clinically indicated.
- 11. A post-dose ECG (within 10 minutes of ending prexasertib infusion) must be obtained on Cycle 1 and Cycle 2. Additional ECG may be obtained if clinically indicated. **NOTE:** it is

- preferred to complete the post-dose ECG upon completion of the prexasertib infusion, but prior to LY3023414 dosing.
- 12. Tumor response by clinical assessment of the patient's disease (ie, by physical examination)

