10 EFFICACY ASSESSMENTS (SOLID TUMOR)

All efficacy assessments will be investigator assessments of response, time to response, and duration of response. Investigator will determine objective response rate, complete response (CR), partial response (PR), stable disease (SD), or progression of disease (PD).

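### ORR is primary and decides the 2-of-10 rule, but no measurable lesion, named response criteria or PR confirmation is required, so ORR can be biased in either direction

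*Combined protocol and SAP*

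**What the plan says.** Section 2.1 sets the primary objective: to "assess the objective response rate (CR+PR) associated with LY3023414 and prexasertib in metastatic TNBC patients". Section 11.4 turns it into a decision. With 0 or 1 responses in 10 patients, enrolment stops. With 2 or more, a further 10 could be added by amendment, if the manufacturer agrees.

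Inclusion criterion 4 in Section 4.2 reads: "Have locoregional (eg, breast, chest wall, regional lymphatic) or pulmonary or hepatic metastatic disease that is amenable to core needle biopsy". It goes on to accept a skin biopsy, and then adds: "If a skin biopsy cannot be safely obtained, patients may still be eligible, per physician discretion". Nothing in Sections 4.2 or 4.3 mentions a measurable lesion or a lesion size.

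Section 10 says only that the "Investigator will determine objective response rate, complete response (CR), partial response (PR), stable disease (SD), or progression of disease (PD". It gives no thresholds, target-lesion rules or confirmation rule. Section 8.2 item 12 lists "Tumor response by clinical assessment" for Day 1 of each cycle, with physical examination as the means. Item 13 asks for CT at eight-week intervals or, as an alternative, when clinically indicated. The matching row of Appendix II gives clinical indication alone.

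Only a clinical CR is described as confirmed (Sections 3, 4.4 and 7.2.2), without an interval. RECIST appears once, in the Section 1.4 background on an ovarian cancer study, where "24 were assessable per protocol and RECIST response".

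**The concern.** ORR is meaningful only if every patient in the denominator could be scored as a responder and every patient in the numerator met a stated standard. The plan secures neither.

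- **Denominator.** Disease that a needle can reach is not necessarily disease that can be measured. Diffuse chest-wall involvement or a small node could satisfy criterion 4 without giving a lesion in which a partial shrinkage can be measured objectively. Such patients would tend to lower ORR.
- **Numerator.** With no criteria and no confirmation of PR, one favourable physical examination can become a response. That would tend to raise ORR.

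A single patient decides between 1 of 10 and 2 of 10, so either mechanism could reverse the decision, and the data would not show which had operated. Duration of response, and the durable-response benchmark of 30% in Section 11.4, rest on the same undefined response and progression.

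**Working it through.** **Inputs from the plan (Section 11.4).** Ten patients, with at least 2 responses needed to continue. For 20 patients, a stated 60% chance of 4 or more responses at a true rate of 20%. Section 1.5 gives a 25% partial response rate for the combination in TNBC.

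**Inputs that are assumptions.** The documents do not give the number of patients k without a measurable lesion, the share f of true non-responders who would be called responders, or a true rate of 10%. I vary k and f.

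**Step 1: the plan's own figure.** P(X ≥ 4), X ~ Binomial(20, 0.20), is 1 − Σ C(20,x)·0.2^x·0.8^(20−x) over x = 0 to 3, which equals 0.589. This agrees with the stated 60% to within about one percentage point. The arithmetic is sound, but it gives all 20 patients the same chance of response.

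**Step 2: downward effect.** Let k of the 10 patients have no chance of being scored a responder and stay in the denominator. Then

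P(X ≥ 2) = 1 − (1−p)^(10−k) − (10−k)·p·(1−p)^(9−k), and expected ORR = p·(10−k)/10.

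For k = 0 and p = 0.20: 1 − 0.8^10 − 10 × 0.2 × 0.8^9 = 1 − 0.1074 − 0.2684 = 0.624.

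| k of 10 | P(≥2), p = 0.20 | Expected ORR, p = 0.20 | P(≥2), p = 0.25 |
|---|---|---|---|
| 0 | 0.624 | 20% | 0.756 |
| 1 | 0.564 | 18% | 0.700 |
| 2 | 0.497 | 16% | 0.633 |
| 3 | 0.423 | 14% | 0.555 |

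With 20 patients and p = 0.20, P(≥4) falls from 0.589 to 0.499 with two such patients and to 0.402 with four.

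**Step 3: upward effect.** If a fraction f of non-responders is called a responder, the observed rate is q = p + (1−p)·f. With p = 0.10:

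- f = 0: q = 0.10, P(≥2 of 10) = 0.264
- f = 0.05: q = 0.10 + 0.90 × 0.05 = 0.145, P(≥2 of 10) = 0.437
- f = 0.10: q = 0.10 + 0.90 × 0.10 = 0.19, P(≥2 of 10) = 0.593

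**Step 4: who is in the denominator.** Section 11.4 counts responses among 10 patients and removes nobody for lack of a measurable lesion, so by default such patients count. Section 11.1.1, however, defines an Evaluable Population by efficacy requirements that are set out nowhere, and says it is assessed for pathologic response, which is not an endpoint of this trial. It uses the ITT population for listings, baseline tables and discontinuations. The stop rule therefore has an implied denominator, and the reported ORR has none.

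**The case against.** The strongest reply has four parts.

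1. A reader might infer that patients without measurable disease can only be non-responders, and so that ORR is biased downward. The documents do not support this. With no criteria in Section 10, the investigator may call a PR in such a patient, and a CR is also possible. The zero response probability in Step 2 is therefore a limiting case, and only the upward effect applies to every patient.
2. The number of such patients may be small. Criterion 4 names sites that often carry measurable lesions. Section 8.1 requires baseline CT within 8 weeks before registration, and the same methods are to be used throughout. The discretion clause most naturally waives obtaining the biopsy, not having disease at one of those sites. All this stands. It limits the denominator problem but does not touch the missing criteria.
3. A reader might infer that the result could not be compared with the 25% rate in Section 1.5. That section does not say which criteria produced the figure, so the inference is unsupported. The ovarian study in Section 1.4 did report by RECIST, but it is background in another tumour and the plan does not use it as a benchmark.
4. Section 11.2 calls the trial exploratory and descriptive. That excuses the absence of a formal test. It does not excuse leaving undefined the quantity being described, which also drives a numerical stopping rule.

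**Conclusion.** The point holds as an endpoint-definition defect that should be corrected. As written, the plan admits patients in whom a PR cannot be measured objectively. It also lets unconfirmed PRs based on examination decide a rule that turns on one response. The direction of the net bias is unknown, and nothing here shows that ORR would be too low or too high overall.

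The size is illustrative. Two unscorable patients in 10 would cut the chance of passing from 62% to 50% at a true 20%. Calling 5% to 10% of non-responders responders would lift it from 26% to between 44% and 59% at a true 10%. Both results depend on assumed values of k, f and the true rate. What rests on the text alone is that there is no measurable-disease criterion, no named response criteria, no confirmation of PR, an inconsistent scan schedule and no stated ORR denominator.

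**What to change.** - **Section 4.2:** add at least one lesion measurable by RECIST 1.1 at baseline.
- **Section 10:** score the ORR endpoint by RECIST 1.1 on imaging, with PR as well as CR confirmed on a subsequent scan. Physical examination can stay in Section 8.2 but should not alone establish the endpoint.
- **Section 8.2 item 13 and Appendix II:** reconcile them so that the scans the endpoint needs are scheduled. Without this, a confirming scan may not exist.
- **Section 11.1.1:** state the ORR denominator, write out the efficacy requirements of the Evaluable Population, and replace the reference to pathologic response with objective response.
- **Sections 3, 4.4 and 7.2.2:** progression and confirmed clinical CR also take patients off treatment, so the endpoint definitions must be reconciled with that wording. When treatment stops is a clinical matter on which this point takes no position.

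The cost is one inclusion criterion, one paragraph in Section 10 and consistency edits. Eligibility becomes slightly narrower, and the confirmed ORR may be slightly lower than an unconfirmed one.
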